 - *What I'm interested in seeing are things that you and your baby are both comfortable with and used to, and things that your baby loves to do.*
 - *Please feel free to move around as is comfortable for you and your baby. You don't have to sit in one place, but I'll need to know what room you'd like to be in so that I can move along with you.*
 - *Attend to any needs your baby might have during this time just as you normally would.*
- **Note:** The purpose of this activity is to encourage the caregiver and child to engage in whatever activity they enjoy and to be as non-restrictive as possible. It is important not to impose any structure on the caregiver above and beyond the instructions. Therefore, do not restrict the caregiver's and child's movement by asking them to stay in one place.
 - *After these 5 minutes, I will give you the instructions for the second part of the recording which lasts 5 minutes. What questions do you have?*
 - **Begin the first 5 minute interaction**

- Record header: *"This is a Mom & Baby Net interaction with family ID # _____; the mother's initials are _____."*
- Tell the participant that we are now beginning the interaction. *You can begin now.*
- After 5 minutes, stop recording and say *Okay, you have finished the first interaction.*

2. **SECOND INTERACTION (5 Minute Looking at Books): Instructions**

- **Place the books near mom and baby so mom can see/reach them:**
1)Brown Bear; 2) Touch and Feel Puppy; 3)Touch and Feel Farm
- Record giving instructions to mom then stop before beginning interaction recording
- Instructions:
 - *During the next five minutes, you and your baby can spend a little time with these books.*
 - *However you want to use the books with your baby is fine.*
 - *Feel free to attend to whatever needs your baby might have.*
 - *What questions do you have?*
- **Record the second interaction**
 - i. Record header: *"This is a Mom & Baby Net interaction with family ID # _____; the mother's initials are _____."*
 - ii. Tell the participant she can begin. *You can begin now.*
 - iii. After 5 minutes, stop recording and say *Thank you! You have finished the video recording piece of the visit.*
 - iv. *Collect 3 assessment books then give 2 participant board books to leave with family.*

BEFORE LEAVING THE HOME

1. Complete iPhone Customization Form
2. Review the **Data Checklist** to ensure all steps and documentation are complete.
 - a. Sprint signal
 - b. Qualtrics Questionnaire, ASRI

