2. Confirm time of call for next day
 - a. Reschedule if necessary (update Access and Matriculation table)

Consent Call (20 minutes) [ASSIGNED COACH]

1. Review consent the same as you would at a home pre-assessment (mom looking along on own copy)
2. Review iPhone agreement the same as you would at a home training visit (mom looking along on own copy)
3. *What other questions do you have about either of these documents or the program?* [answer questions]
4. *Are you still interested in participating?*
 1. If yes: *Great! Please go ahead and sign both pages. As soon as we get off the phone, take a picture of every page (even those that don't have a signature) and text them to the number I am calling from ####-####-####.*
 2. If no: *I am sorry to hear that. Can I ask why you changed your mind?*
5. Explain drop off or mailing of phone/accessories/manual
 1. *The next step is to drop off or mail your iPhone, accessories, and materials. We will sanitize all materials before getting them to you. In the bag you will find two baby books, your Mom and Baby Net handbook, iPhone, charger, headphones, and a tripod stand. Inside your Mom and Baby Net handbook in the front pocket of the binder, you will find a card with information about how to connect on Zoom.*
 2. If dropping off (if they have experienced issues getting UPS packages, this will be the best option): *To minimize contact and keep with social distancing, I will call once I have arrived outside and parked. I will remain on the phone with you, place your bag at the door, and let you know when to retrieve it. While you are on the phone, we will select a time for us to have our next call.*
 3. If mailing: *I will track the package and call or text to confirm it has arrived.*
6. Explain Zoom Training & Preassessment calls

1. *After you receive everything, we will have another call. We will connect via Zoom video chat and you will get an instruction card for that in your materials. Once you are familiar using Zoom, that's how we will communicate for the rest of the program. Also, on that call, we will record 2 5-minute videos of you and [baby's name] playing together and looking at some books that we will send. We will also begin the surveys, which are split into 2 parts. We will likely not finish everything on one call, so we will go ahead and schedule 2 separate calls for the same week.*
7. Ask mom some questions to determine the best time and way to complete the pre assessment remotely

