 3. *What I'm interested in seeing are things that you and your baby are both comfortable with and used to, and things that your baby loves to do.*
 4. *Please feel free to move around as is comfortable for you and your baby but make sure that both you and your baby are visible on the screen at all times.*
 5. *Attend to any needs your baby might have during this time just as you normally would.*
 6. *After these 5 minutes, I will stop recording then I will give you the instructions for the second part of the recording which lasts 5 minutes. What questions do you have?*

7. Answer any questions mom has.
8. Stop recording on Zoom.

- ii. Record Free Play Video
 1. Give mom time to finish setting up for the video and confirm that she is ready.
 2. Coach should record using Speaker View and have the running time visible (or use a timer on your phone) set to make sure you get a minimum of 5:30 minutes of recording.
 3. *I am going to start recording, say an intro sentence for the video, then ask you to begin.*
 4. Select 'record' on Zoom
 5. *This is an interaction video with participant [say ID #], the mother's initials are [say mom's initials]*
 6. To mom: *You can begin now.* Coach – mute your microphone to mute your own background noise.
 7. After 5:30 minutes, stop recording on Zoom, unmute yourself, and say *Ok, the first video is finished.* Allow the mom to transition. *Now we will do the second video.*

- d. Books video (use Color and Animal baby books given to all moms)
 - i. Record Book video instructions
 1. Select record on Zoom
 2. *During the next five minutes, you and your baby can spend a little time with these books.*
 3. *However you want to use the books with your baby is fine.*
 4. *Feel free to attend to whatever needs your baby might have.*
 5. *What questions do you have?*
 6. Answer any questions mom has.
 7. Stop recording on Zoom.
 - ii. Record Books Video
 1. Give mom time to finish setting up for the video and confirm that she is ready.
 2. Coach should record using Speaker View and have the running time visible (or use a timer on your phone) set to make sure you get a minimum of 5:30 minutes of recording.
 3. *I am going to start recording, say an intro sentence for the video, then tell you to begin.*
 4. Select 'record' on Zoom
 5. *This is an interaction video with participant [say ID #], the mother's initials are [say mom's initials]*

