 4. *Please feel free to move around as is comfortable for you and your baby but make sure that both you and your baby are visible on the screen at all times.*
 5. *Attend to any needs your baby might have during this time just as you normally would.*
 6. *After these 5 minutes, I will stop recording then I will give you the instructions for the second part of the recording which lasts 5 minutes. What questions do you have?*
 7. Answer any questions mom has.
 8. Stop recording on Zoom.
- ii. Record Free Play Video
 1. Give mom time to finish setting up for the video and confirm that she is ready.
 11. Coach should record using Speaker View and have the running time visible (or use a timer on your phone) set to make sure you get a minimum of 5:30 minutes of recording.
 2. *I am going to start recording, say an intro sentence for the video, then tell you to begin.*
 3. Select 'record' on Zoom
 4. *This is an interaction video with participant [say ID #], the mother's initials are [say mom's initials]*

5. To mom: *You can begin now.* Coach – mute your microphone to mute your own background noise.
6. After 5:30 minutes, stop recording on Zoom, unmute yourself, and say *Ok, the first video is finished.* Allow the mom to transition. *Now we will do the second video.*
- d. Books videos (use Color and Animal baby books given to all moms at pre-assessment or appropriate board/soft books mom has at home)
 - i. Record Book video instructions
 1. Select record on Zoom
 2. *During the next five minutes, you and your baby can spend a little time with these books.*
 3. *However you want to use the books with your baby is fine.*
 4. *Feel free to attend to whatever needs your baby might have.*
 5. *What questions do you have?*
 6. Answer any questions mom has.
 7. Stop recording on Zoom.
 - ii. Record Books Video
 1. Give mom time to finish setting up for the video and confirm that she is ready.
 12. Coach should record using Speaker View and have the running time visible (or use a timer on your phone) set to make sure you get a minimum of 5:30 minutes of recording.
 13. *I am going to hit record, say an intro sentence for the video, then tell you to begin.*
 14. Select 'record' on Zoom
 15. *This is an interaction video with participant [say ID #], the mother's initials are [say mom's initials]*
 16. To mom: *You can begin now.* Coach – mute your microphone to mute your own background noise.

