(Aims 2.1 - 2.3) Our post-assessment n, to examine acute intervention effects, is expected to be 150 (75/condition). We will initially view intervention effects on our mother/infant outcomes using a 2 (pre-post) $\times 2$ (MBN intervention group) repeated measure analysis of variance. We will examine the inter-correlations among outcomes and, if significant, will use a MANOVA approach to examining MBN intervention effects. The F test is robust to non-normality if such non-normality is caused by skewness rather than outliers. We will take appropriate measures to reduce outlier influences. **(Aim 2.4)** To examine the relations between mother change (parenting and maternal depression) and infant change, one approach will be to create individual beta estimates for mothers and infant utilizing the polynomial contrast function within MANOVA to produce individual trajectory scores reflecting parent and infant change from pre to post that can then be used in external between-condition covariate analysis. The trajectory scores will be subjected to an analysis of covariance with infant change trajectories as the dependent variable and parent change as the covariate. We will determine whether the parent change covariate is significantly related to the dependent variable (demonstrating that changes in parenting behavior and child functioning covary). We will determine the statistical significance and effect sizes of intervention effects (ignoring the covariate). We will then determine if entering the parent functioning covariate modifies the intervention effect size and statistical significance. If parent change is strongly linked to infant change, then entering the covariate should result in nonsignificant intervention effects. Estimates of covariance-adjusted effect sizes will provide estimates of the proportion of intervention effect size that can be explained by the parenting change variable. We will test for between-group heterogeneity of covariance to determine whether the strength of association between change in parenting and infant functioning differs by intervention group.

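### The filmed book and free-play tasks are not held constant from pre to post, which adds noise to observational change scores and can pass for mother–infant covariation in Aim 2.4

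*Protocol*

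**What the plan says.** **Home procedure (Protocol section II, Record the Interactions).** The book task uses a named set, "1)Brown Bear; 2) Touch and Feel Puppy; 3)Touch and Feel Farm". Afterwards the assessor is told: "Collect 3 assessment books then give 2 participant board books to leave with family". In free play the assessor moves with the dyad, and the note to staff says "It is important not to impose any structure on the caregiver above and beyond the instructions".

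**Remote procedure (Protocol section VI).** The Consent Call tells the mother what will arrive before baseline: "In the bag you will find two baby books, your Mom and Baby Net handbook". The Pre-Assessment Call films her with them: "Books video (use Color and Animal baby books given to all moms". She keeps them through a 14-session program. Under Schedule Post Assessment, the coach asks whether she still has them. If not, suitable books from the home may be used, and books are mailed if there are none. The Post Assessment Call lists the project books "or appropriate board/soft books mom has at home" without giving an order. In remote free play the mother sets up the phone herself and is asked to "make sure that both you and your baby are visible on the screen at all times".

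**Crossover.** The remote post scripts refer back to a first home visit, so dyads with a home pre and a remote post were expected.

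**Analysis.** The SAP is dated September 2016. Its Constructs paragraph puts questionnaire scales and observational codes into the mother and infant outcomes. Aims 2.1–2.3 use a 2 (pre-post) × 2 (group) repeated-measures ANOVA. Aim 2.4 regresses infant change on parent change in an ANCOVA, and a significant covariate is taken as "demonstrating that changes in parenting behavior and child functioning covary". Neither model has a term for mode or book set. The Assessment Data Checklist has no field for which books were used.

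**The concern.** A pre-post change score measures change in behavior only if the task is the same both times. Here some dyads meet a different set of books, a different degree of familiarity with them and a different camera arrangement at post. Their observed change mixes parenting change with task change.

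Two analyses are exposed. First, the observational change scores become noisier, which costs power in Aim 2. Second, Aim 2.4 rests on individual differences in change. If switching task raises or lowers both the mother's and the infant's video-based scores, dyads that switched differ from dyads that did not on both variables at once. The ANCOVA, which holds only condition constant, can report that as parent and infant change being linked.

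**Working it through.** **1. Who meets which task**

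| Pathway | Books at pre | Books at post | Free-play camera |
|---|---|---|---|
| Home–home | three assessor books, collected | the same three | assessor follows, both times |
| Home–remote | three assessor books, collected | two kept books, or own books | assessor, then phone set up by mother |
| Remote–remote | two project books | the same two, now familiar, or own books | phone, both times |

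The documents do not give the share in each pathway or the effect of a task change on scores. Both are assumptions below.

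**2. The SAP's own power figures.** Inputs are N = 150, m = 2 occasions, alpha .05, and pre-post r = .68 or .21. The noncentral F for the group × time term has noncentrality f²·N·m/(1−r), with f = d/2 and 1 and 148 df. Power at the stated effects is:
- d = .37, r = .21: .948 (SAP .95)
- d = .23, r = .68: .938 (SAP .95)
- d = .29, r = .21: .802 (SAP .80)
- d = .18, r = .68: .782 (SAP .80)

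The SAP's figures are reproduced to within two points, so the same formula can serve for step 5.

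**3. The randomized contrast.** Let q be the share of dyads whose task shifts and s the shift in SD, equal in both arms. Within-arm change moves by q·s, from .10 × .2 = 0.02 SD to .50 × .5 = 0.25 SD. The arm difference has expected error zero. Chance imbalance in q, with 75 per arm, leaves an SD of s·√(2q(1−q)/75). At q = .50 and s = .5 this is .5 × √(.50/75) = .5 × .0816 = 0.041 SD, or at most about ±0.08 SD with 95% probability. At q = .10 and s = .2 the SD is 0.010.

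**4. Spurious covariation in Aim 2.4.** Suppose a share p is home–remote, the switch moves the mother and infant composites by δ each (in SDs of the change score), and the two are otherwise unrelated. The covariance is c = p(1−p)δ² and each variance is 1 + c, so r = c/(1+c). The rejection rate at two-sided .05 follows from Fisher's z with n = 150. With p = .25, p(1−p) = .1875:

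| δ | c | spurious r | false positives |
|---|---|---|---|
| .2 | .0075 | .007 | 5.1% |
| .4 | .030 | .029 | 6.4% |
| .5 | .047 | .045 | 8.4% |
| .8 | .120 | .107 | 26% |
| 1.0 | .188 | .158 | 49% |

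At p = .10 and δ = .5 the rate is 5.8%. δ is the shift in the whole composite, so questionnaire content makes it smaller than the shift in the video codes.

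**5. Noise.** As an outer bound, suppose the task change pulled the pre-post correlation from the top of the SAP's range to the bottom. At d = .20, the low end expected for infants, the noncentrality is .01 × 300/(1−r):
- r = .68: 9.38, power .86
- r = .50: 6.00, power .68
- r = .21: 3.80, power .49

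Nothing in the documents says the drop would be this large.

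**The case against.** The strongest reply is that randomization deals with the problem. Both arms follow the same book and filming rules under 1:1 allocation, so a common shift cancels in expectation from the group × time test. That stands, and step 3 shows the chance remainder is small.

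A reader might still infer that MBN mothers rehearse on the test books under coaching, so that the arm contrast is biased. The coach guides do differ: MBN calls review the mother's video for infant signals and program skills, while comparison calls watch two pause points and discuss milestones. But both arms have weekly calls around a mother-made video, both keep the same books, and no text says that session videos or practice use them. Arm-specific rehearsal is possible, not documented.

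A reader might also take the 26% and 49% rows as the expected error. They need shifts of 0.8 to 1 SD in whole composites, equal and in the same direction for mother and infant, with no true covariation and no shift in remote–remote dyads. The SAP does not say how much of the infant outcome comes from video.

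Two further replies stand in part. Own books are a fallback under Schedule Post Assessment, although the Post Assessment Call is looser. Free-play instructions are similar in both modes, and home filming also aims to keep both faces in frame. The camera arrangement still differs, but no effect on scores is shown.

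**Conclusion.** The task is not constant from pre to post, and the SAP has no term that would absorb the difference. The consequence is limited to observational outcomes for dyads with a remote post-assessment. It takes the form of added noise and possible spurious mother–infant covariation in Aim 2.4. It is not a demonstrated bias in MBN versus DDAS.

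The size cannot be fixed from the documents. With p = .25, n = 150 and no true covariation, moderate composite shifts of 0.2 to 0.5 SD give roughly 5% to 8% false positives against a nominal 5%. Single-indicator outcomes (maternal depression, knowledge, stress) are not touched by the filmed tasks. This is a worthwhile, inexpensive improvement and not a threat to the trial's main comparison.

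**What to change.** 1. **Hold the books constant.** Delete the own-book option in Schedule Post Assessment and in the Post Assessment Call. Film each remote post with the titles that dyad was filmed with at pre, mailing a copy when the mother does not have them. Sending the three home books to every remote dyad would be worse, because remote–remote dyads would then change titles between pre and post.
2. **Record the task.** Add book set and mode to the Assessment Data Checklist. For completed assessments, code them from the saved, dated videos.
3. **Aim 2.4.** Add assessment pathway (home–home, home–remote, remote–remote) as a factor in the ANCOVA.
4. **Observational Aim 2 outcomes.** Keep the planned group × time test as primary. Report one sensitivity analysis adding pathway × time and one restricted to same-mode, same-book dyads. State that post mode is partly settled after randomization, since post is scheduled at session 14 or the last coach call. Neither sensitivity analysis should therefore replace the primary test.

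The cost is postage for some dyads (the plan already mails books when needed), two degrees of freedom and one sensitivity table. Remote–remote dyads will still know their books better at post than at pre. These steps do not remove that, and it should be reported as a limitation.
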